### 8.3. Exploratory Efficacy Analyses

Summaries and analysis of immunogenicity and cellular assay data will be presented for the ITT population. If there are major protocol deviations (as defined in Section 6.3.2) or if any subjects are found to be ineligible at baseline, a per-protocol (PP) analysis may also be performed.

Cellular assay data represent the percent of CD4+ and CD8+ T-Cells expressing each cytokine or combination of cytokines. For each endpoint, the standard deviation (SD) of the percent of cells at baseline will be calculated on a log scale across all groups combined. An individual positive response is then defined as the log percent of cells at a follow-up visit more than 3 SD greater than the baseline log percent.

Positive responses to each ANDV peptide pool (PP1, PP2) or to either pool, will be summarized. Intracellular cytokine (ICS) data will be presented by CD4+ and CD8+ T-Cell responses secreting each cytokine and cytokine combination. T-Cell lymphoproliferation (LPA) responses will be presented separately for CD4+ and CD8+ T-Cells. Measurements will be taken on Day 29 (3 and 4 dose regimen), Day 57 (3 dose regimen), Day 85 (4 dose regimen), Day 169 (3 and 4 dose regimen), and Day 197 (3 and 4 dose regimen). ICS results are presented in [Table 33](#) through [Table 44](#) and graphically for each cytokine combination in [Figure 17](#), [Figure 18](#) (IFN $\gamma$ ), [Figure 19](#), [Figure 20](#) (TNF $\alpha$ ), [Figure 21](#), [Figure 22](#) (IL-2), [Figure 23](#), [Figure 24](#) (IFN $\gamma$  and TNF $\alpha$ ), [Figure 25](#), [Figure 26](#) (IFN $\gamma$  and IL-2), [Figure 27](#), [Figure 28](#) (TNF $\alpha$  and IL-2), [Figure 29](#), and [Figure 30](#) (IFN $\gamma$ , TNF $\alpha$  and IL-2). LPA results are presented in [Table 45](#) and [Table 46](#) and graphically in [Figure 31](#) and [Figure 32](#).

Immune responses in terms of a titer  $\geq 20$  in antibody post vaccination, measured by PsVNA and PRNT will be summarized for additional time points. The additional time points for PsVNA are Day 29, Day 85, and Day 169. The additional time point for PRNT is Day 169. These results are presented in [Table 19](#), [Table 20](#), [Table 21](#), and [Table 22](#) and graphically in [Figure 11](#), [Figure 12](#), [Figure 13](#), and [Figure 14](#).

Reverse cumulative distributions (RCD) curves will be presented for PRNT and PsVNA antibody titers. The plots are shown in [Figure 3](#), [Figure 4](#), [Figure 5](#), and [Figure 6](#).

Box-and Whisker graphs of PsVNA and PRNT antibody titers will be plotted on a log scale over time, by vaccination group at each time point ([Figure 7](#), [Figure 8](#), [Figure 9](#), and [Figure 10](#)).

The Spearman correlation between PsVNA and PRNT titers will be evaluated and presented in [Table 31](#) and [Table 32](#). The correlation will be depicted in scatter plots as [Figure 15](#) and [Figure 16](#).

Data listings of ICS and LPA assay results as reported by the laboratory will be provided in [Listing 7](#). Listings will be sorted by vaccination group, subject ID, and visit.

No formal hypothesis testing is planned.

## 9. SAFETY EVALUATION

### 9.1. Demographic and Other Baseline Characteristics

Summaries of age, sex, ethnicity, and race will be presented by vaccination group and overall ([Table 16](#) and [Table 17](#)). Ethnicity is categorized as Hispanic or Latino, or not Hispanic and not Latino. In accordance with NIH reporting policy, subjects may self-designate as belonging to more than one race or may refuse to identify a race, the latter reflected in the CRF as “No” to each racial option.

Individual subject listings will be presented for all demographics ([Listing 5](#)).

#### 9.1.1. Prior and Concurrent Medical Conditions

Complete medical history is obtained by interview of subjects at the screening visit and is reviewed and/or updated on Day 1 prior to study vaccination. At follow-up visits after study vaccination, an interim medical history is obtained by interview of subjects noting any changes since the previous clinic visit or contact. The interim medical history should include an assessment for new medical conditions. Subjects are queried regarding a history of significant medical disorders of the head, eyes, ears, nose, throat, mouth, cardiovascular system, lungs, gastrointestinal tract, liver, pancreas, kidney, urologic system, nervous system, blood, lymph nodes, endocrine system, musculoskeletal system, skin, and genital/reproductive tract. A history of any allergies, cancer, immunodeficiency, psychiatric illness, substance abuse, and autoimmune disease is solicited.

All current illnesses and past pre-existing medical conditions will be MedDRA® coded using MedDRA dictionary version 22.0 or higher. Summaries of subjects’ pre-existing medical conditions will be presented by vaccination group ([Table 18](#)).

Individual subject listings will be presented for all medical conditions ([Listing 6](#)).

#### 9.1.2. Prior and Concomitant Medications

Medication history (concomitant medications) includes a review of all current medications and medications taken within 60 days prior to signing the ICF through approximately 28 days after the last study vaccination or early termination (if prior to 28 days after the last study vaccination), whichever occurs first. Medications reported in the eCRF are limited to those taken within 30 days prior to the first study vaccination through approximately 28 days after the last study vaccination. Prescription and over-the-counter drugs are included as well as herbals, vitamins, and supplements. Use of new medication should prompt evaluation for the occurrence of any AE.

Summaries of medications that were started prior to dosing or continuing at the time of dosing will be presented by WHO Drug Terms 2 and 3 and vaccination group ([Table 147](#)).

Individual subject listings will be presented for all concomitant medications ([Listing 16](#)).

### 9.2. Measurements of Treatment Compliance

The subject disposition table ([Table 12](#)) will summarize the number of subjects that were screened, randomized, received at least one treatment, received all scheduled treatments, completed all blood draws, completed Study Day 197, and completed follow-up (Study Day 337).

Individual subject listings will be presented for all subjects who discontinued dosing ([Listing 1](#)).

## 9.3. Adverse Events

When calculating the incidence of adverse events (i.e., on a per subject basis), each subject will only be counted once and any repetitions of adverse events within a subject will be ignored; the denominator will be the number of subjects in the Safety population. All adverse events reported will be included in the summaries and analyses.

An overall summary of adverse events is presented in [Table 47](#).

Adverse events occurring in 5% of subjects in any vaccination group will be presented in [Table 48](#).

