### 6.3.3. Safety Population

The Safety Analysis population includes all subjects who received at least one dose of study vaccine.

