### 9.3.1. Solicited Events and Symptoms

Systemic solicited adverse events are collected pre-vaccination, and systemic and local solicited adverse events are collected 30 minutes post-vaccination and then daily for 7 days after each vaccination and graded on a scale of 0 (absent), 1 (mild), 2 (moderate) and 3 (severe). See [Table 5](#), [Table 6](#), [Table 7](#), [Table 8](#), and [Table 9](#) for additional grading details. Systemic events include fever, feverishness, fatigue, malaise, myalgia, nausea, dizziness and headache. Local events include pain, tenderness, erythema, induration, ecchymosis, and skin discoloration. If a subject experiences the same local adverse event in both arms for a given vaccination, then the greatest severity between arms will be reported.

The proportion of subjects reporting at least one solicited adverse event will be summarized for each solicited adverse event, any systemic symptom, any local symptom, and any symptoms. The 95% CI calculated using Clopper-Pearson methodology from a binomial distribution (SAS Proc Freq with a binomial option) will be presented. These results are presented in [Table 49](#), [Table 50](#), [Table 51](#), [Table 52](#), and [Table 53](#).

For each systemic and local event, any systemic event, any local event, and any solicited event, the maximum severity over 7 days after each vaccination will be summarized for the Safety population. The number and percentage of subjects reporting each event, as well as the 95% CI calculated using Clopper-Pearson methodology, will be summarized by the maximum severity and vaccination group, separately for each vaccination and over all vaccinations. For each event, the denominator is the number of subjects with non-missing data for the specific event ([Table 54](#), [Table 55](#), [Table 56](#), [Table 57](#), and [Table 58](#)).

The number of subjects reporting each solicited adverse event will be summarized for each day post vaccination for each vaccination and for all vaccinations, both in summary tables starting with [Table 59](#) and ending with [Table 80](#) and graphically starting with [Figure 33](#) and ending with [Figure 42](#).

Solicited adverse events by subject will be presented in [Listing 9](#) and [Listing 10](#).

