### 9.3.2. Unsolicited Adverse Events

The proportion of subjects reporting at least one unsolicited adverse event will be summarized by MedDRA system organ class and preferred term for each vaccination and over all vaccinations. Denominators for percentages are the number of subjects in the Safety population who received the vaccination being summarized.

Unsolicited adverse events by subject will be presented in [Listing 11](#).

The following summaries for unsolicited adverse events will be presented by MedDRA system organ class, preferred term, dose and vaccination group:

- Incidence and 95% CI of unsolicited adverse events after each dose and any time during the study will be summarized in [Table 81](#), [Table 82](#), [Table 83](#), [Table 84](#), and [Table 85](#);

- The total frequency of unsolicited adverse events after each dose and any time during the study will be summarized in [Table 86](#) and [Table 87](#);
- Summary of severity and relationship to study product after dose 1 and dose 2 ([Table 88](#), [Table 89](#), and [Table 90](#));
- Summary of severity and relationship to study product after dose 3 and dose 4 and at any time ([Table 91](#), [Table 92](#), [Table 93](#), [Table 94](#), [Table 95](#), and [Table 96](#));
- Incidence and 95% CI of unsolicited adverse events related to IP, after each dose and any time during the study will be summarized in [Table 97](#), [Table 98](#), [Table 99](#), [Table 100](#), and [Table 101](#);
- The total frequency of unsolicited adverse events related to IP, after each dose and any time during the study will be summarized in [Table 102](#) and [Table 103](#);
- Subject listing of SAEs ([Table 104](#));
- Bar chart of the total frequency of non-serious related unsolicited adverse events by severity and MedDRA system organ class ([Figure 43](#), [Figure 44](#), [Figure 45](#), [Figure 46](#), and [Figure 47](#));
- Bar chart of the incidence of non-serious related unsolicited adverse events by maximum severity and MedDRA system organ class ([Figure 48](#), [Figure 49](#), [Figure 50](#), [Figure 51](#), and [Figure 52](#));

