Any PT	x (x)	x	x	x	x	x	x	x	x	x	x	x	x	x	x	x	
[PT 1]																	
Etc.																	
[SOC 1]																	
Any PT	x (x)	x	x	x	x	x	x	x	x	x	x	x	x	x	x	x	
[PT 1]																	
Etc.																	

N=Number of subjects in the Safety Population (number of subjects at risk).

n=Number of subjects reporting any solicited or unsolicited adverse event.

Events=total frequency of events reported.

**14.3.1.1      Solicited Adverse Events****Table 49:      Number and Percentage of Subjects Experiencing Solicited Events with 95% Confidence Intervals by Symptom, Dose, and Vaccination Group - Post Dose 1**

Symptom	Cohorts 1 + 2 ANDV DNA 2 mg (N=X)		Cohorts 3 + 4 ANDV DNA 4 mg (N=X)		All Placebo (N=X)		All Subjects (N=X)	
	n (%)	95% CI	n (%)	95% CI	n (%)	95% CI	n (%)	95% CI
Any Symptom								
Any Systemic Symptom								
Feverishness								
Malaise								
Fatigue								
Myalgia								
Headache								
Nausea								
Dizziness								
Fever								
Any Local Symptom								
Pain								
Tenderness								
Erythema								
Erythema (Measurement)								
Induration								
Induration (Measurement)								
Skin Discoloration								
Ecchymosis								
Ecchymosis (Measurement)								

Note: N=Number of subjects in the Safety Population; n=Number of subjects experiencing the symptom.

Table with similar format:

**Table 50: Number and Percentage of Subjects Experiencing Solicited Events with 95% Confidence Intervals by Symptom, Dose, and Vaccination Group - Post Dose 2**

**Table 51: Number and Percentage of Subjects Experiencing Solicited Events with 95% Confidence Intervals by Symptom, Dose, and Vaccination Group - Post Dose 3**

Symptom	ANDV DNA 2mg				ANDV DNA 4mg				Placebo			
	Cohort 1 3 Doses (N=X)		Cohort 2 4 Doses (N=X)		Cohort 3 3 Doses (N=X)		Cohort 4 4 Doses (N=X)		All Placebo (N=X)		All Subjects (N=X)	
	n (%)	95% CI	n (%)	95% CI	n (%)	95% CI						
Any Symptom												
Any Systemic Symptom												
Feverishness												
Malaise												
Fatigue												
Myalgia												
Headache												
Nausea												
Dizziness												
Fever												
Any Local Symptom												
Pain												
Tenderness												
Erythema												
Erythema (Measurement)												
Induration												
Induration (Measurement)												
Skin Discoloration												
Ecchymosis												
Ecchymosis (Measurement)												

Table with similar format:

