**Table 52: Number and Percentage of Subjects Experiencing Solicited Events with 95% Confidence Intervals by Symptom, Dose, and Vaccination Group - Post Dose 4**

**Table 53: Number and Percentage of Subjects Experiencing Solicited Events with 95% Confidence Intervals by Symptom, Dose, and Vaccination Group - Post Any Dose**

Symptom	ANDV DNA 2mg				ANDV DNA 4mg				Placebo			
	Cohort 1 3 Doses (N=X)		Cohort 2 4 Doses (N=X)		Cohort 3 3 Doses (N=X)		Cohort 4 4 Doses (N=X)		All Placebo (N=X)		All Subjects (N=X)	
	n (%)	95% CI	n (%)	95% CI	n (%)	95% CI						
Any Symptom												
Any Systemic Symptom												
Feverishness												
Malaise												
Fatigue												
Myalgia												
Headache												
Nausea												
Dizziness												
Fever												
Any Local Symptom												
Pain												
Tenderness												
Erythema												
Erythema (Measurement)												
Induration												
Induration (Measurement)												
Skin Discoloration												
Ecchymosis												
Ecchymosis (Measurement)												

**Table 54: Number and Percentage of Subjects Experiencing Solicited Events by Symptom, Maximum Severity, Dose, and Vaccination Group - Post Dose 1**

Symptom	Severity	Cohorts 1 + 2 ANDV DNA 2 mg (N=X)		Cohorts 3 + 4 ANDV DNA 4 mg (N=X)		All Placebo (N=X)		All Subjects (N=X)	
		n (%)	95% CI	n (%)	95% CI	n (%)	95% CI	n (%)	95% CI
Any Symptom	None	x (x.x)	x.x, x.x	x (x.x)	x.x, x.x	x (x.x)	x.x, x.x	x (x.x)	x.x, x.x
	Mild								
	Moderate								
	Severe								
Repeat for:									
Any Systemic Symptom									
Feverishness									
Malaise									
Fatigue									
Myalgia									
Headache									
Nausea									
Dizziness									
Fever									
Any Local Symptom									
Pain									
Tenderness									
Erythema (Severity)									
Erythema (Measurement)									
Induration (Severity)									
Induration (Measurement)									
Skin Discoloration									
Ecchymosis (Severity)									
Ecchymosis (Measurement)									

Note: N=Number of subjects in the Safety Population who received the specified dose; n=Number of subjects experiencing the symptom. Severity is the maximum severity reported over all solicited symptoms post dosing for each subject.

\*Does not include measurements.

Table with similar format:

**Table 55: Number and Percentage of Subjects Experiencing Solicited Events by Symptom, Maximum Severity, Dose, and Vaccination Group - Post Dose 2**

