		Moderate							
		Severe							
Repeat for									
Post Dose 2 (N = X)									
Post Dose 1 or 2 (N = X)									

Note: N=Number of subjects in the Safety Population; n=Number of subjects experiencing an AE within the SOC and PT combination. Severity is the maximum severity reported post dosing for each subject for each day.

Tables with similar format:

**Table 89: Frequency and Percent of Subjects with Unsolicited Adverse Events by MedDRA System Organ Class and Preferred Term, Maximum Severity, and Relationship – ANDV DNA 4 mg - Post-Doses 1 and 2**

**Table 90: Frequency and Percent of Subjects with Unsolicited Adverse Events by MedDRA System Organ Class and Preferred Term, Maximum Severity, and Relationship – Placebo - Post-Doses 1 and 2**

**Table 91: Frequency and Percent of Subjects with Unsolicited Adverse Events by MedDRA System Organ Class and Preferred Term, Maximum Severity, and Relationship – ANDV DNA 2 mg (3 Doses) - Post-Dose 3 and 4, and At Any Time**

MedDRA System Organ Class	Preferred Term	Severity	Events Related to IP		Events Not Related to IP		Any Event		
			n	%	n	%	n	%	
Post Dose 3 (N = X)									
Any SOC	Any PT	Any Severity	x	xx	x	xx	x	xx	
		Mild							
		Moderate							
		Severe							
SOC 1	PT 1	Any Severity							
		Mild							
		Moderate							
		Severe							
	PT 2	Any Severity							
		Mild							
		Moderate							
		Severe							
Repeat for									
Post Dose 4 (N = X)									
Any Time (N = X)									

Note: N=Number of subjects in the Safety Population; n=Number of subjects experiencing an AE within the SOC and PT combination. Severity is the maximum severity reported post dosing for each subject for each day.

 Any AE reported post-dose 1.

Tables with similar format:

**Table 92: Frequency and Percent of Subjects with Unsolicited Adverse Events by MedDRA System Organ Class and Preferred Term, Maximum Severity, and Relationship – ANDV DNA 2 mg (4 Doses) - Post-Dose 3 and 4, and At Any Time**

**Table 93: Frequency and Percent of Subjects with Unsolicited Adverse Events by MedDRA System Organ Class and Preferred Term, Maximum Severity, and Relationship – ANDV DNA 4 mg (3 Doses) - Post-Dose 3 and 4, and At Any Time**

**Table 94: Frequency and Percent of Subjects with Unsolicited Adverse Events by MedDRA System Organ Class and Preferred Term, Maximum Severity, and Relationship – ANDV DNA 4 mg (4 Doses) - Post-Dose 3 and 4, and At Any Time**

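### For solicited events after doses 2 to 4, SAP 9.3 divides by subjects who may never have had the dose, and two sets of tables would report the same symptom on different denominators

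*SAP*

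**What the plan says.** SAP 6.3.3 defines the population: "The Safety Analysis population includes all subjects who received at least one dose of study vaccine". A subject who stops after dose 1 therefore stays in it.

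Three denominator rules follow in the text.

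- SAP 9.3, for adverse-event incidence in general: "the denominator will be the number of subjects in the Safety population".
- SAP 9.3.1, for solicited events by maximum severity (Tables 54 to 58): "the denominator is the number of subjects with non-missing data for the specific event". The paragraph on Tables 49 to 53, which give incidence with exact intervals, names no denominator.
- SAP 9.3.2, for unsolicited events: "Denominators for percentages are the number of subjects in the Safety population who received the vaccination being summarized".

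The table shells in SAP Appendix 1 do not settle it.

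- Table 49 (solicited, post dose 1) has the footnote "Note: N=Number of subjects in the Safety Population; n=Number of subjects experiencing the symptom". Table 50 (post dose 2) copies its format. Tables 51 to 53 carry no footnote.
- Table 54 (maximum severity, post dose 1) says "N=Number of subjects in the Safety Population who received the specified dose". Table 55 copies its format. Tables 56 to 58 carry no footnote.
- Tables 88, 91 and 96 (unsolicited, by severity and relationship, in per-dose blocks) say "N=Number of subjects in the Safety Population; n=Number of subjects experiencing an AE within the SOC and PT combination". Tables 89, 90 and 92 to 95 copy them.

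**The concern.** Solicited events after each vaccination are a primary outcome (SAP 3.2.1), and the trial tests no hypothesis (SAP 6.8), so the percentages and their exact intervals are the result. Protocol 5.4.3 allows subjects to stop vaccination and remain in follow-up. Some of the listed reasons are reactions to the product: a related serious event, generalized urticaria, or a Grade 3 event lasting 24 hours or more.

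Under the 9.3 rule, such a subject counts after every later dose as someone without a symptom, although no dose was given. The later-dose rate is then too low. If stops of this kind are more common on vaccine than on placebo, the vaccine–placebo contrast shrinks as well. The report would also show two percentages and two intervals for one symptom after one dose, for example in Tables 52 and 57.

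**Working it through.** **Inputs.** Vaccine groups have 10 subjects (9 randomized plus 1 sentinel, SAP Table 1). Tables 49 and 50 pool the regimens, giving 20 per dose level; Tables 51 and 52 show each group of 10. Intervals are Clopper-Pearson 95% (SAP 9.3.1). Neither document gives a missed-dose rate, so the numbers missed below are assumptions.

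**The plan's own figures.** SAP Table 3 gives the chance of at least one event, 1 − (1 − p)^n. For p = 10%: n = 10 gives 1 − 0.9^10 = 65.1%, and n = 20 gives 1 − 0.9^20 = 87.8%. All 18 cells reproduce. They are computed at 10 and 20 subjects; with 8 recipients the first becomes 1 − 0.9^8 = 57.0%.

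**Which rule governs which table**

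| Tables | Content | Text rule | Footnote |
|---|---|---|---|
| 50 | Solicited, dose 2, with CI | Safety population (9.3) | Safety population |
| 51–52 | Solicited, doses 3–4, with CI | Safety population (9.3) | none |
| 55 | Same symptoms, dose 2, by severity, with CI | Non-missing data (9.3.1) | Dose recipients |
| 56–57 | Same symptoms, doses 3–4, by severity, with CI | Non-missing data (9.3.1) | none |
| 81–84 | Unsolicited, per dose, with CI | Recipients (9.3.2) | Dose recipients |
| 88–96 | Unsolicited, per dose, no CI | Recipients (9.3.2) | Safety population |

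Tables 50 to 52 disagree with Tables 55 to 57 on the same quantity. Table 55 also disagrees with its own text, and Tables 88 to 96 with theirs.

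**Size.** The rate is x/n. The limits are the 2.5% quantile of Beta(x, n − x + 1) and the 97.5% quantile of Beta(x + 1, n − x).

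Three events in a group of 10:

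| Assumed | Safety population | Dose recipients | Non-missing data |
|---|---|---|---|
| Nothing missed | 3/10 = 30.0% (6.7–65.2) | same | same |
| 1 dose missed | 30.0% (6.7–65.2) | 3/9 = 33.3% (7.5–70.1) | same as recipients |
| 2 doses missed | 30.0% (6.7–65.2) | 3/8 = 37.5% (8.5–75.5) | same as recipients |
| 2 doses missed, 1 recipient without data | 30.0% (6.7–65.2) | 37.5% (8.5–75.5) | 3/7 = 42.9% (9.9–81.6) |

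With no events, the upper limit is 30.8% for 0/10, 33.6% for 0/9 and 36.9% for 0/8.

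In the pooled post-dose-2 table the effect is smaller: 6/20 = 30.0% against 6/19 = 31.6% with one missed dose, and 30.0% (11.9–54.3) against 6/18 = 33.3% (13.3–59.0) with two.

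**Interval width.** At low and middle counts the Safety-population interval is too narrow: about 59 points for 3/10 against 67 for 3/8. When nearly every recipient has the symptom, the width reverses: 8/10 gives 80.0% (44.4–97.5), while 8/8 gives 100% (63.1–100). The rate is still too low, and the interval is misplaced.

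**The case against.** The best reply is that 9.3 is a general rule and 9.3.1 and 9.3.2 are specific ones. The 9.3 sentence stands directly above Tables 47 and 48, which are any-time summaries and for which it is right. SAP 6.1 bases percentages on the non-missing sample size and labels columns with the population relevant to the period, and a subject who missed dose 4 has no post-dose-4 diary. The SAP expects little missing data (6.5). Table 12, Listing 1 and Listings 9 to 11 would let a reader rebuild any denominator.

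Much of this stands. It does not rescue Tables 50 to 52. No specific rule covers them, the 9.3 sentence is the more particular statement on adverse-event incidence, and the footnote that Table 50 inherits repeats it. For Tables 51 and 52 the case rests on the 9.3 text alone. Few missing data does not mean few missed doses, and listings do not correct a printed percentage.

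A reader might infer that every per-dose adverse-event rate counts non-recipients. The documents do not support that. Section 9.3.2 and the footnotes of Tables 81 and 83 limit unsolicited per-dose rates to recipients, and Tables 97 to 103 take their formats from Tables 81, 83, 86 and 87. The by-day solicited tables follow the Table 59 footnote, which also uses recipients. Nor would intervals conflict in Tables 88 to 96: those shells have none, and because they print a separate N for each dose block, the footnote may simply be incomplete.

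**Conclusion.** The conflict is real and has a limited reach. It concerns solicited events after doses 2 to 4 (Tables 50 to 52 against 55 to 57) and, by footnote only, the post-dose 2 to 4 blocks of Tables 88 to 96. Dose 1 is not exposed to the missed-dose error, because everyone in the Safety population received a first dose. For any-dose summaries the Safety population is the suitable denominator.

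Under the assumed miss counts, a 30.0% rate in a group of 10 should read 33.3% with one missed dose and 37.5% with two. If no dose and no assessment is missed, there is no difference at all. The point deserves correction because a stated rule gives wrong primary-outcome percentages and intervals whenever a later dose is missed, and because the choice should not be left until the data are unblinded.

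**What to change.** - In SAP 9.3, limit the Safety-population denominator to any-time and any-dose summaries: Tables 47, 48, 53, 58 and 85, and the any-time blocks of other tables.
- Add that per-dose tables use Safety-population subjects who received that dose and, for solicited events, those with at least one assessment after it.
- Change the denominator sentence in 9.3.1 to match. Correct the footnotes of Tables 49, 50, 54 and 55, and add one to Tables 51, 52, 56 and 57.
- Bring the footnotes for the per-dose blocks of Tables 88 to 96 into line with 9.3.2.
- Leave Tables 81 to 84 and 97 to 103 as they are.

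The cost is wording and footnotes, with no new data or procedures. Some later-dose intervals become slightly wider.
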